## **Events Not to Be Considered as Serious Adverse Events**

Elective hospitalizations to administer or to simplify study treatment or procedures are not considered as SAEs.

Any death occurring greater than 30 days after the last dose of the investigational agent/intervention requires expedited reporting within 24 hours only if it is possibly, probably, or definitely related to the investigational agent/intervention.

### **14.2. Pregnancy and In Utero Drug Exposure**

The investigator will attempt to collect pregnancy information if a female patient or a male patient's female partner becomes pregnant while the patient is participating in this study. The pregnancy information will be recorded on the appropriate form and must be submitted to the sponsor within 2 weeks of learning of the pregnancy. The patient or partner will be followed for the outcome of the pregnancy. Information on the status of the mother and child will be forwarded to the sponsor or designee. Generally, follow up will be no longer than 6 to 8 weeks following the estimated delivery date. Any premature termination of the pregnancy will be reported.

### **14.3. Severity**

Investigators must evaluate the severity/intensity of AEs according to the NCI-CTCAE v4 current active minor version, preferentially using the graded scales. If a particular AE's severity/intensity is not specifically graded, the investigator should apply the general guidelines for determination of Grade 1 through Grade 5 as listed in the NCI-CTCAE v4 current active minor version, cover page (reproduced below), using their best medical judgment:

**Grade 1:** Mild; asymptomatic or mild symptoms; clinical or diagnostic observations only; intervention not indicated.

**Grade 2:** Moderate; minimal, local or noninvasive intervention indicated; limiting age-appropriate instrumental activities of daily living (preparing meals, shopping for groceries or clothes, using the telephone, managing money, etc.).

**Grade 3:** Severe or medically significant but not immediately life-threatening; hospitalization or prolongation of hospitalization indicated; disabling; limiting self-care activities of daily living (bathing, dressing and undressing, feeding self, using the toilet, taking medications, and not bedridden).

**Grade 4:** Life-threatening consequences; urgent intervention indicated.

**Grade 5:** Death related to AE.

### **14.4. Relationship to Study Drug**

Investigators must also assess the causal relationship of each AE to dalantercept/placebo and axitinib. Factors for the assessment of causal relationship include, but are not limited to, temporal relationship between the AE and the administration of dalantercept/placebo or axitinib, known side effects of dalantercept/placebo or axitinib, medical history, concomitant therapy, course of the underlying disease and pertinent study procedures.

- Probably:** A causal relationship is clinically/biologically highly plausible and there is a plausible time sequence between onset of the AE and administration of dalantercept/placebo or axitinib and there is a reasonable response on withdrawal.
- Possibly:** A causal relationship is clinically/biologically plausible and there is a plausible time sequence between onset of the AE and administration of dalantercept/placebo or axitinib.
- Unlikely:** A causal relationship is improbable and another documented cause of the AE is most plausible.
- Not Related:** A causal relationship can be definitively excluded and another documented cause of the AE is most plausible.

## **14.5. Documentation and Methods of Reporting of Adverse Events by Investigator**

Patients will be evaluated and questioned generally for AEs during the course of the study, starting at the signing of the informed consent. All non-serious AEs occurring after signing of the ICF until a patient is dosed on C1D1 are to be documented on the medical history CRF. All AEs occurring after the C1D1 dose through 30 days after the last study drug administration (final visit) are to be documented on the AE CRF.

All AEs spontaneously reported by the patient and/or in response to an open question from study personnel or revealed by observation, physical examination or other diagnostic procedures will be recorded on the AE CRF. Any clinically relevant changes in laboratory assessments, or other clinical findings as described in [Section 14.1](#), are considered AEs and must be recorded on the AE CRF. AEs are to be followed for resolution as described in [Section 14.6](#).

It is important that each AE report include a description of the event, duration (onset and resolution dates), severity, relationship with dalantercept/placebo, relationship with axitinib, any other potential causal factors, any treatment given or other action taken (including dose modification or discontinuation of dalantercept or axitinib) and outcome. In addition, SAEs should be identified and the appropriate seriousness criteria documented. Adverse events categorized as SAEs must also be documented using an SAE Report Form as described in [Section 14.5.1](#).

Specific guidance can be found in the CRF Completion Guidelines provided by the sponsor or designee.

### **14.5.1. Documentation of Serious Adverse Events**

All SAEs that occur after the first study drug administration on C1D1 until 30 days (final visit) after the last study drug administration are to be documented on the AE CRF. SAEs should not be reported for patients who are considered screen failures unless the event is deemed due to a protocol required procedure. For all SAEs, an SAE form must be completed with as much information as possible and submitted within the time frame described in [Section 14.7](#) (Notification about Serious Adverse Events).

When new significant information is obtained as well as when the outcome of an event is known, the investigator should record the information on a new SAE form. If the patient was hospitalized, a copy of the discharge summary must be included as part of the patient medical

file. In all instances, the investigator should follow up with patients until the outcome of the SAE is known.

#### **14.6. Reporting Period and Monitoring of Patients with Adverse Events**

All patients who took at least one dose of study drug should complete the final visit procedures. All AEs will be followed until clinical database lock (or stabilization/resolution if it occurs before database lock). All SAEs will undergo active follow-up until resolved or the event becomes chronic or stable. Follow-up data for SAEs obtained after clinical database lock will be incorporated into the dalantercept safety database.

#### **14.7. Notification about Serious Adverse Events**

If an SAE occurs during the reporting period, the investigator must immediately (i.e. within a maximum 24 hours after becoming aware of the event) inform the sponsor via the CRO by telephone, by fax or by e-mail.

All written reports should be transmitted using the study specific SAE Report Form, which must be completed by the investigator following specific completion instructions. Names, addresses, telephone and fax numbers for SAE reporting are located on the SAE Report Form and in the completion instructions provided in the Study Reference Manual. When an SAE (or follow-up information) is reported by telephone, a written report must be sent immediately thereafter by fax or e-mail. Reporting procedures and timelines for follow-up information are the same as for the initially reported SAE.

Relevant pages from the CRF may be provided in parallel (i.e., medical history, concomitant therapy). In all cases, the information provided in the SAE Report Form must be consistent with the data that are recorded in the corresponding sections of the CRF.

The investigator/reporter must respond to any request for follow-up information or to any question the sponsor or designee may have on the SAE within the same timelines as described for initial reports. This is necessary to permit a prompt assessment of the event by the sponsor and (as applicable) to allow the sponsor to meet regulatory timelines associated with expedited reporting obligations.

For Part 1, requests for follow-up will usually be made by the responsible CRA or medical monitor, or in exceptional circumstances by the Acceleron or CRO Pharmacovigilance representative who may contact the investigator directly to obtain clarification on a particularly critical event. For Part 2, requests for follow-up will be made by the CRO Pharmacovigilance representative who may contact the investigator directly to obtain clarification on a particularly critical event.

##### **14.7.1. Safety Reporting to Health Authorities, Independent Ethics Committees Institutional Review Boards and Investigators**

The sponsor will send appropriate blinded or unblinded (as applicable) safety notifications to Health Authorities in accordance with applicable laws and regulations.

The investigator must comply with any applicable site-specific requirements related to the reporting of SAEs involving his/her patients to the IEC/IRB that approved the study.

In accordance with ICH/GCP guidelines, the sponsor will inform the investigator of “findings that could adversely affect the safety of patients, impact the conduct of the study, or alter the IRB’s approval/favorable opinion to continue the study.”

The sponsor will inform the investigator of AEs that are both serious and unexpected and are considered to be related to dalantercept (“suspected unexpected serious adverse reactions” or SUSARs). The investigator should place copies of these Safety Reports in the Investigator Site File. National regulations with regard to Safety Report notifications to investigators will be followed.

When specifically required by regulations and guidelines, the sponsor will provide appropriate Safety Reports directly to each site who is responsible for notifying their IRB and will maintain records of these notifications. When direct reporting by the sponsor is not clearly defined by national or site-specific regulations, the investigator will be responsible for promptly notifying the concerned IRB of any Safety Reports and for filing copies of all related correspondence in the Investigator Site File.

For studies covered by the European Union Clinical Trials Directive 2001/20/EC, the sponsor’s responsibilities regarding the reporting of SAEs/SUSARs will be carried out in accordance with that Directive and with the related Detailed Guidances.

## 15. STATISTICS

### Statistical Methods:

#### Study Design Overview

A dose escalation plus expansion cohort design to evaluate the safety of dalantercept plus axitinib will be implemented to determine the recommended Phase 2 dose level of dalantercept for Part 2 of the trial.

Part 2 is a randomized placebo-controlled trial in previously treated advanced RCC patients. The randomization will be stratified by prior mTOR therapy and prior immune therapy. The primary endpoint for statistical analysis is PFS defined as the time from randomization to documented progression or death based on the investigator assessment.

#### Analysis Populations:

The **All Treated (AT) Population** includes all patients who received any study drug. The AT is the population that will be used when performing the primary analysis of the primary endpoint and all safety analyses. The AT population will be analyzed according to treatment received.

The **Full Analysis Set (FAS)** includes all randomized patients. The intent-to-treat principle will be used for this study population. The FAS will be used in secondary analyses of the primary endpoint.

The **Pharmacokinetics (PK) population** will consist of all patients who received at least 1 dose of dalantercept and axitinib and have sufficient PK samples collected and assayed.

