**Statistical Analysis:**

Details regarding the final data analysis will be discussed in a separate Statistical Analysis Plan (SAP).

The primary analysis of PFS will be based on investigator assessment using the AT population. Time to radiographic progression or death is the primary efficacy analysis and will be performed using a stratified (by prior treatment) log-rank test.

A log-rank test stratified by prior mTOR and immune therapy will be used to test the null hypothesis of no difference between dalantercept plus axitinib and placebo plus axitinib using a one-sided 0.10 significance level. Kaplan-Meier curves will be displayed depicting each treatment group. The hazard ratio (dalantercept plus axitinib: placebo plus axitinib) will be estimated using a stratified Cox proportional hazards model along with the 95% confidence intervals.

For the secondary PFS objective in the subgroup of patients who had 2 or more prior lines of anticancer therapy, the stratified log-rank test will be performed at one-sided 0.20 significance level due to a smaller sample size.

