### **10.3. Randomization and Blinding**

**Part 1:** This is an open-label dose escalation that does not require randomization.

**Part 2:** Patients will be randomized to receive 0.9 mg/kg of dalantercept or placebo plus axitinib 5 mg PO BID. Randomization assignments will be generated through a computerized system, provided by an Interactive Web Response System (IWRS). Patients who have signed informed consent and met all eligibility criteria will be stratified according to prior mTOR therapy and prior immune therapies. Patients will then be randomly assigned to dalantercept or placebo plus axitinib within each stratum.

Only the pharmacist or his/her designee who prepares the study drug (dalantercept or placebo) and an unblinded clinical research associate at the CRO will be unblinded to the patient treatment assignments. All other study personnel, including but not limited to Investigators, study coordinators, nursing staff, clinical monitors, the Sponsor, and the Sponsor's representatives, will remain blinded to the study treatment assignments.

In the event of a medical emergency for an individual patient in which knowledge of the study drug is critical to the patient's medical management, the investigator may break the blind for that patient. However, prior to breaking the blind, every effort must be made by the investigator to first discuss the need to break the blind with the medical monitor. Further, it must be determined by the investigator that breaking the treatment blind is necessary information for the medical management of that patient. If the blind is broken, investigator discretion, in consultation with the medical monitor as needed, should be used to determine if the patient should continue on treatment or be discontinued from the study.

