### 15.2. Determination of Sample Size

#### Part 1

There is no formal sample size calculation for Part 1 (dose escalation and expansion).

#### Part 2

The primary analysis of efficacy will be performed when at least 82 PFS events have been observed and documented. If the median time to PFS is assumed to be 5 months in the placebo plus axitinib control group, then a total of 82 PFS events will provide approximately 80% power to detect a 3 month extension from 5 to 8 months in the dalantercept plus axitinib experimental treatment group when performing a stratified log-rank test of the null hypothesis of no difference between treatment groups using a one-sided 10% significance level.

The projection of power is made under a proportional hazards assumption so that the hazard ratio (HR) for dalantercept plus axitinib relative to placebo plus axitinib is equal to 0.625 under the alternative hypothesis. It is projected that 130 patients will need to be randomized to obtain 82 PFS events. The number of patients to be randomized provides for patient censoring patterns that could occur under the alternative hypothesis in the event the dropout rate is higher than expected in either treatment group.

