### **15.4. Part 2 – Efficacy and Safety**

#### **15.4.1. Primary Endpoint**

**Progression free survival:** PFS is the primary endpoint in Part 2 and will be defined as the date of radiographic (also called documented) tumor progression (per RECISTv1.1) or death from any cause, whichever is earliest, minus date of randomization (or first date of dosing in Part 1 as will be implied throughout) plus one day. The term “on-study” will refer to the period from randomization until 28 days after last dose of study medication. Patients will be censored (i.e., those patients not exhibiting radiographic tumor progression or death) on the date of the last tumor assessment on-study and includes:

- Those patients discontinuing study medication due to any reason and having at least 1 radiographic tumor assessment before or on the date of discontinuation
- Those patients in whom radiographic tumor progression or death occurs following  $\geq 2$  consecutive scheduled missing radiographic tumor assessments
- Those patients given non-study antitumor medication or treatment prior to documentation of radiographic tumor progression

Patients missing baseline radiographic tumor assessments will be censored on the date of randomization. Patients with missing post-randomization radiographic tumor assessments will be censored on the date of randomization unless death occurred prior to the first and second scheduled radiographic tumor assessment, whereby death is the event.

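### The primary PFS test uses dosed patients grouped by treatment received although an intent-to-treat set is already defined; making that set primary is a cheap safeguard with a small expected effect

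*Combined protocol and SAP*

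**What the plan says.** The Synopsis and Section 15 (Analysis Populations) agree. On the AT set: "The AT is the population that will be used when performing the primary analysis of the primary endpoint and all safety analyses", and "The AT population will be analyzed according to treatment received". The FAS contains everyone randomized and follows intent-to-treat, but its role is limited: "The FAS will be used in secondary analyses of the primary endpoint". The Synopsis (Statistical Analysis) and Section 15.4.1 repeat the choice: "The primary analysis of PFS will be based on investigator assessment using the AT population".

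The rest of the design is built on randomization. Section 15 (Study Design Overview) has "PFS defined as the time from randomization to documented progression or death based on the investigator assessment". Section 15.2 has "It is projected that 130 patients will need to be randomized to obtain 82 PFS events". The log-rank test is stratified by the randomization factors. The document gives no reason for preferring AT.

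Three other passages bear on the size of the problem. Section 10.3 lists the investigators, other site staff and the sponsor among those who "will remain blinded to the study treatment assignments". Section 12.2 asks that randomization ideally fall within 48 hours of the first dosing day. Section 15.4.1 says: "Patients with missing post-randomization radiographic tumor assessments will be censored on the date of randomization unless death occurred prior to the first and second" scheduled assessment.

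**The concern.** Randomization makes the arms comparable as assigned. AT changes membership and grouping by events that come later: a patient who is never dosed drops out of the deciding test, and a patient given the wrong product moves to the other arm. If either happens more in one arm, or differently by prognosis, the comparison is no longer the randomized one.

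The bias can run both ways. Losing early-event patients only from the dalantercept arm flatters dalantercept; losing them only from placebo works against it. The secondary FAS analysis would show a discrepancy, but the AT result would still decide the trial.

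**Working it through.** **1. The plan's own figure.** Inputs from Section 15.2: hazard ratio (HR) 0.625, one-sided 0.10, 80% power; 1:1 allocation from Section 9.1.

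- Events = 4(z₀.₉₀ + z₀.₈₀)² / (ln 0.625)² = 4(1.2816 + 0.8416)² / 0.4700² = 81.6, so 82.
- Power at 82 events = Φ(√82/2 × 0.4700 − 1.2816) = Φ(2.128 − 1.282) = 0.801.

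The plan reproduces. The choice of population is a separate matter from the sample size.

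**2. Simulation of AT against FAS.** The document gives no undosed or misdosed counts, so every count here is an assumption. Setting: 65 per arm, exponential PFS, control median 5 months, 12-month uniform accrual (assumed), analysis at 82 events in the set analysed, unstratified log-rank test, 40,000 trials per case (Monte Carlo standard error about 0.0015 for error, 0.002 for power). Undosed patients are drawn from those with a PFS event before day 84, and their events are taken as recorded in the FAS. With no deviations, error is 0.101 and power 0.794.

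One-sided error at nominal 0.10, for 1/2/3 undosed early-event patients:

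| Lost from | AT | FAS |
|---|---|---|
| Either arm, regardless of assignment | 0.098/0.103/0.101 | 0.098/0.102/0.100 |
| Dalantercept only | 0.117/0.136/0.161 | 0.099/0.099/0.102 |
| Placebo only | 0.087/0.077/0.062 | 0.101/0.102/0.099 |

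With 1% or 2% of each arm given the other product at random, error is 0.100/0.098 for AT and 0.101/0.099 for FAS.

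Power at HR 0.625:

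- Losses regardless of arm (1/2/3 patients): AT 0.796/0.801/0.797, FAS 0.794/0.798/0.797.
- Misdosing of 1%/2% of each arm: AT 0.796/0.799, FAS 0.782/0.773.

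**3. How often the two sets disagree.** At HR 0.625, with losses regardless of arm and one common data cutoff, the pass/fail decisions differ in about 2.7%/3.3%/3.9% of trials for 1/2/3 undosed patients.

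**4. Power if undosed patients are followed and have no treatment effect.** Dilute the log hazard ratio by (1 − m/130), where m is the number undosed:

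- m = 1: Φ(2.128 × 129/130 − 1.282) = 0.797
- m = 2: 0.792
- m = 3: 0.787
- m = 3, all in the dalantercept arm, factor (1 − 3/65): Φ(2.030 − 1.282) = 0.773

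**5. Which undosed patients the swap affects.** Under Section 15.4.1, an undosed patient who is alive and has no scan after randomization is censored at randomization and contributes nothing to either analysis. Only recorded early deaths and available scans matter. For scans, the section ends the on-study period 28 days after the last dose, a date that undosed patients do not have.

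**The case against.** The strongest reply is that in the situation the protocol supports, blinded allocation with prompt dosing, AT and FAS have the same error and the same power, and under misdosing the FAS has slightly less power. The FAS analysis is prespecified, so a discrepancy would be reported, and further sensitivity analyses are deferred to a separate SAP. All of this stands, and it is why the point is minor. It does not settle which analysis governs when the two disagree, and that is best fixed in advance.

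Four stronger readings are tempting.

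- **The plan's error rate is 0.12 to 0.16.** A reader might infer this from the dalantercept-only row. Those figures assume that every loss comes from one arm and is chosen by its outcome. They also let any PFS event before day 84 stand in for early death, which covers 1 − 2^(−2.76/5) = 32% of patients at a 5-month median (84 days = 2.76 months). Section 9.3.1 requires a life expectancy of at least 12 weeks, so real counts should be lower. The document names no reason for a one-arm pattern.
- **Disagreement reaches nearly 6%.** Cutting each set at its own 82nd event gives 3.2%/4.8%/5.7%, but this mixes a shift of the data cutoff into the population effect. Disagreement also does not show that the AT result is the wrong one.
- **Part 1 must change too.** Section 15.3 already names AT as its primary population, and Part 1 is not randomized.
- **A new duty to collect survival data is needed.** Section 14.6 ties final-visit procedures to at least one dose. However, the Schedule of Events asks patients who terminate to complete that visit without a dosing condition, and Section 15.4.2 times overall survival from randomization and asks for reasonable effort to establish status.

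**Conclusion.** The point holds as a minor, inexpensive improvement. The primary PFS comparison is not the randomized one, although the set that would make it so is already defined. The document supports no claim that the 0.10 level is generally lost: with losses unrelated to arm, error is about 0.10 and power about 0.80 in both sets. Under an assumed one to three undosed early-event patients, the choice of set changes the decision in about 3% to 4% of trials at HR 0.625. Losses from one arm only (AT error about 0.12 to 0.16 for dalantercept, 0.06 to 0.09 for placebo) are a conditional worst case, not the error rate of the plan.

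These sizes rest on assumed counts, exponential PFS, 12-month accrual and an unstratified test. That AT is primary and the FAS secondary is certain from the text.

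**What to change.** For Part 2:

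- In the Synopsis (Analysis Populations, Statistical Analysis), Section 15 (Analysis Populations) and Section 15.4.1, make the FAS the primary PFS population, analysed as randomized with the randomization strata, and count the 82 events in it.
- Keep AT by treatment received for safety and as a supportive PFS analysis. The subgroup PFS test follows, because Section 15.4.2 ties it to the primary analysis.
- In Section 15.4.1, state that for randomized but undosed patients the on-study period is counted from randomization. Recorded deaths and available scans can then enter the FAS analysis under the existing censoring rules, including the rule for non-study antitumor treatment. Undosed patients who are alive without a post-randomization scan stay censored at randomization.

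Part 1 needs no change. The 82 events and 130 patients stand.

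The cost is these wording edits and a small possible loss of power: to about 0.77 to 0.78 if 1% to 2% of each arm is misdosed, or to about 0.787 to 0.797 if one to three undosed patients are followed and have no treatment effect (about 0.773 if all three are in the dalantercept arm).
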